Duration of Objective Response (DOR) is the time between first objective response of CR or PR and the first date that progressive disease is objectively documented or death. Patients who do not experience objective PD or death will not be included in the analysis.

Time to first objective response is the time from first dose of study drug to first objective response of CR or PR. Patients who do not experience objective response of CR or PR will be censored at the last adequate assessment date.

PFS is defined as the time (number of months) from date of first dose of study drug until date of documented disease progression or death due to any cause, whichever comes first. More specifically, PFS will be determined using all the assessment data up until the last evaluable visit prior to or on the date of (i) radiographic or clinical disease progression; (ii) withdrawal of consent to obtain scans; or (iii) receiving subsequent anticancer therapy, whichever is earlier. Death is always categorized as a confirmed PD event. Censoring methods for patients who do not experience PD or death will be described in the study SAP.

OS is calculated as the time (number of months) from date of first dose of study drug to the date of death due to any cause. Patients who do not experience fatalities during the course of the study will be censored at the date last known to be alive. Patients lacking data beyond the day of first dose of G1T38 will have their survival time censored at day of first dose. OS will not be censored if a subject receives other antitumor treatments after the study drugs.

The BOR, ORRs, and CBR and their corresponding 95% exact CIs will be calculated by Clopper-Pearson method. DOR, time to first objective response, PFS, and OS will be analyzed based on time-to-event summary method. For PFS and OS, Kaplan-Meier estimates will be plotted and tabulated at selected landmark time points (ie, 6 months, 1 year, 1.5 years, and 2 years).

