PD	Unequivocal progression of existing NTLs. Unequivocal progression is defined as, “an overall substantial worsening in nontarget disease, such that, even in the presence of SD or PR in target lesions, the overall tumor burden has increased sufficiently to merit discontinuation of therapy. A modest “increase” in size of one or more nontarget lesions is usually not sufficient to qualify for unequivocal progression status

G1 Therapeutics, Inc.
 Clinical Study Protocol G1T38-03
 Statistical Analysis Plan

NE	Only relevant when one or some of the NTLs have not been assessed and in the Investigator's opinion they are not able to provide an evaluable overall NTL assessment.
----	---

New lesions

New lesions will be identified via a Yes/No tick box. The absence and presence of new lesions at each visit should be listed alongside the TL and NTL visit responses.

A new lesion indicates progression so the overall visit response will be PD irrespective of the TL and NTL response.

Time Point Response (TPR)

[Table 3-1](#) defines how the previously defined TL and NTL responses will be combined with new lesion information to give an overall response at each time point. The possible overall responses at a visit are CR, PR, SD, PD, and NE.

Table 3-1 Evaluation of Overall Response at Each Time Point – patients with target lesion(s)			
Target Lesions	Non-target Lesions	New Lesions	Overall Response
CR	CR	No	CR
CR	Non-CR/Non-PD	No	PR
CR	Not evaluated	No	PR
PR	Non-PD/not all evaluated	No	PR
SD	Non-PD/not all evaluated	No	SD
NE	Non-PD	No	NE
PD	Any	Yes or No	PD
Any	PD	Yes or No	PD
Any	Any	Yes	PD

CR = complete response, PR= partial response, SD = stable disease, PD = progressive disease,

NE = not evaluable

Source: ([Eisenhauer et al, 2009](#))

For patients without any target lesion, [Table 3-2](#) defines how the previously defined NTL responses will be combined with new lesion information to give an overall response at each time point. The possible overall responses at a visit are CR, Non-CR/Non-PD, PD, and NE.

Table 3-2 Evaluation of Overall Response at Each Time Point – patients without target lesion(s)		
Non-target Lesions	New Lesions	Overall Response
CR	No	CR
Non-CR/Non-PD	No	Non-CR/Non-PD
NE	No	NE
PD	Yes or No	PD
Any	Yes	PD

CR = complete response, PD = progressive disease, NE = not evaluable

Source: ([Eisenhauer et al, 2009](#))

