Unconfirmed objective response (OR_{UNCONFIRMED}) will be derived as No/Yes (0/1) variable. Patients with a BOR of confirmed CR, confirmed PR, unconfirmed CR or unconfirmed PR will be assigned “Yes”. All patients with other BOR values will be assigned “No”. Hence, ORR_{UNCONFIRMED} is defined as the proportion of patients with OR_{UNCONFIRMED} being “Yes”.

Disease Control Rate at Week 8

Disease control rate (DCR) at Week 8 is defined as the proportion of patients with a BOR of confirmed CR or confirmed PR or SD or Non-CR/Non-PD at 8 weeks. For patients without measurable lesions at baseline, a BOR of Non-CR/Non-PD will be considered achieving disease control.

Duration of Objective Response

Duration of objective response (DOR) is the time between first objective response of CR or PR and the first date that progressive disease (PD) is objectively documented or death. Patients who experienced an objective response but who do not experience objective PD or death at the time of analysis will be censored at the last adequate assessment date. Adequate assessment is defined as there is sufficient data to evaluate a patient’s disease status. DOR will be calculated only for patients who experience a confirmed objective response.

Time to First Objective Response

Time to first objective response is the time from first dose of once-daily dosing of G1T38 (Cycle 1 Day 1) to first objective response of CR or PR. This variable will be calculated only for patients who experience a confirmed objective response.

Progression-free Survival

Progressive disease (PD) is defined as radiographical determined disease progression based on the criteria by RECIST Version 1.1, which is also referred to as “documented disease progression” in the SAP. PD status is derived from the radiographical assessments by investigators that have been entered to the EDC. A PFS event is defined as a PD event or a death due to any cause.

PFS is defined as the time (months) from start date of continuous daily of G1T38 (i.e. Cycle 1 Day 1) to the date of the first documented PFS event, and the time from start date of continuous daily of G1T38 to the censoring date for those patients that did not experience a PFS event. That is, PFS is calculated as (date of PFS event or censoring – start date of continuous daily of G1T38 + 1)/

G1 Therapeutics, Inc.
Clinical Study Protocol G1T38-03
Statistical Analysis Plan

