30.4375. In general the date of PD will be determined using all radiographical assessment data up until the last adequate visit prior to or on the date of (i) disease progression as defined by RECIST Version 1.1, (ii) withdrawal of consent, or (iii) receiving subsequent anti-cancer therapy, whichever is earlier. The “adequate visit” is defined as the visit when all scheduled tumor assessments have been performed. Specifically, if PD and new anti-cancer therapy occurred on the same day for a patient, it is assumed that the PD occurred first.

The primary PFS analysis is to assess PFS before treatment discontinuation. PFS will also be evaluated including tumor assessment data post the last dose of study drug (denoted as the secondary PFS analysis). The censoring rules for the primary PFS analysis are provided in [Table 5-1](#), while the censoring rules for the secondary PFS analysis are presented in [Table 5-2](#).

Table 5-1 PFS Calculation and Censoring Rules for the Primary PFS Analysis

Situation	Date of PD Event or Censored	Outcome
Incomplete or no baseline tumor assessments	Date of Cycle 1 Day 1	Censored
No progression	Date of the last adequate radiological disease assessment with no documented disease progression	Censored
Treatment discontinuation for reasons other than disease progression	Date of the last adequate radiological disease assessment with no documented progression	Censored
New anticancer treatment started prior to documented disease progression	Date of last adequate radiologic assessment no later than the initiation of new anticancer treatment	Censored
Disease progression per RECIST Version 1.1	Date of the first documented progression	PFS event
Death in the absence of documented PD	Date of death	PFS event

Table 5-2 PFS Calculation and Censoring Rules for the Secondary PFS Analysis

Situation	Date of PD Event or Censored	Outcome
Incomplete or no baseline tumor assessments	Date of Cycle 1 Day 1	Censored
No progression	Date of the last adequate radiological disease assessment with no documented disease progression	Censored

G1 Therapeutics, Inc.
Clinical Study Protocol G1T38-03
Statistical Analysis Plan

Treatment discontinuation for reasons other than disease progression, and disease progression documented post last dose of study drug	Date of the last adequate radiological disease assessment	PFS event

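### SAP 4.1.2.1 gives conflicting rules for dating progression in the PFS analyses and defines an adequate assessment in two different ways

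*SAP*

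**What the plan says.** All of the following is in SAP 4.1.2.1 unless stated otherwise.

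- **PFS narrative.** After the words In general, it says that "the date of PD will be determined using all radiographical assessment data up until the last adequate visit" on or before the earliest of RECIST progression, consent withdrawal or new anticancer therapy. An adequate visit "is defined as the visit when all scheduled tumor assessments have been performed".
- **Definition of progression for PFS.** "PD status is derived from the radiographical assessments by investigators that have been entered to the EDC". No complete visit is required.
- **Table 5-1 (primary PFS).** RECIST progression is an event on the "Date of the first documented progression". Adequacy appears only in censoring rows, for example "Date of the last adequate radiological disease assessment with no documented disease progression".
- **Table 5-2 (secondary PFS, which adds scans after the last dose).** If treatment stopped for another reason and progression was documented later, the patient has an event, dated at the last adequate scan.
- **Response rules.** Table 1 makes a target-lesion visit not evaluable only when progression cannot be judged from the lesions that were measured. The missing-data rule still gives progression when there is a new lesion or non-target progression. For new lesions: "A new lesion indicates progression so the overall visit response will be PD irrespective of the TL and NTL response".
- **Duration of response.** Here an adequate assessment is one with enough information to judge the patient's disease state.
- **Protocol 12.3.2.** "PFS will be determined using all the assessment data up until the last evaluable visit prior to or on the date of" progression, consent withdrawal or new therapy. The term evaluable is not defined there.

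**The concern.** Whether the scan set was complete matters for a negative visit: a patient should not be declared progression-free on half a scan set. It does not matter for a positive one, since a new brain lesion is progression whether or not the abdomen was imaged that day. The narrative applies the completeness test to the data that date progression and so does not separate the two cases.

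Partial scans that show progression are foreseeable. Protocol 10.1 asks sites to image any location where new disease is suspected and to send in unscheduled scans, and Protocol Table 9-1 makes follow-up brain imaging conditional on indication.

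A programmer who applies the narrative first and Table 5-1 second could drop such a progression from PFS while best overall response counts it. In the secondary analysis, Table 5-2 could keep the event but date it too early. One-year PFS is a named secondary objective in SAP 2.1.

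**Working it through.** The plan states no figure on this point, so the check is mainly a reading of the text.

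**Step 1. One case through each rule.** Treatment continues, the week-16 scan set is complete and negative, and a symptom-driven brain MRI alone at week 20 shows a new lesion.

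| Rule | Result |
|---|---|
| Time point response | Progression at week 20 |
| Table 5-1 | PFS event at week 20 |
| Narrative, literal | Week 20 is not a complete visit, so the data stop at week 16; no progression in the data used |
| Narrative with the duration-of-response definition | Week 20 is adequate; PFS event at week 20 |

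The narrative with its own definition gives a different answer from the other three. The SAP does not say whether narrative or table prevails.

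**Step 2. The same MRI after treatment stopped for another reason.** Table 5-2 gives an event dated at the last adequate scan: week 16 under the strict definition, week 20 under the looser one. With scans every 8 weeks (12 after month 18), and if the previous scheduled visit was complete, the error is up to 56/30.4375 = 1.84 months (84/30.4375 = 2.76 months). It shortens PFS, the opposite direction to Step 1.

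**Step 3. Illustration of the primary analysis.** Assumptions:
- exponential PFS with median 10.1 months (the Part 2 control value in Protocol 12.1, borrowed)
- scans every w = 1.84 months
- data cut at 24 months
- a share q of progressions first seen on a partial scan. No document gives q; 10% to 30% is assumed.

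Probability of progressing in one scan interval: p = 1 − exp(−ln 2 × 1.84/10.1) = 0.1186. The last scan before 12 months is the sixth, at 6 × 1.84 = 11.04 months.

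- Table 5-1 reading: 12-month PFS = (1 − p)^6 = 46.9% for every q.
- Literal narrative, patient censored at the previous complete scan: the Kaplan-Meier hazard per scan is h = (1 − q)p/(1 − qp), and 12-month PFS = (1 − h)^6.
- Literal narrative, but a complete scan one interval later shows the progression: 12-month PFS = (1 − p)^6 + q[(1 − p)^5 − (1 − p)^6], with (1 − p)^5 = 53.2%.

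| q | h | Censored early | Event one interval late |
|---|---|---|---|
| 10% | 0.1080 | 50.4% | 47.5% |
| 20% | 0.0972 | 54.1% | 48.1% |
| 30% | 0.0861 | 58.3% | 48.8% |

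A simulation of 20,000 patients gave 46.8% for the Table 5-1 reading, 50.2%, 53.9% and 57.8% for early censoring, and 47.5%, 47.9% and 48.6% for the late event. Medians fall on the scan grid: 11.0 months under Table 5-1; 12.9, 12.9 and 14.7 months with early censoring; 11.0 months with the late event.

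**The case against.** The strongest reply is that the SAP already contains the right rule. It names Table 5-1 as the rules for the primary analysis, and that table makes RECIST progression an event without a completeness test. The narrative opens with In general, and its window "using all radiographical assessment data up until the last adequate visit prior to or on the date of (i) disease progression" presupposes that progression has been identified; using the window to exclude that same progression would be circular. This stands as the more sensible reading. It does not settle the matter, because the narrative says which data fix the progression date, the table says what to do with that date, and no precedence is stated. Nor does it answer Table 5-2, where adequacy dates an event.

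A reader might infer that the SAP simply discards progression on partial or unscheduled scans and censors those patients earlier. The documents do not support that. Table 5-1 says otherwise. The adequacy definition concerns completeness, not whether the visit was planned, and an unscheduled visit with a full scan set could qualify. Even on the literal reading, a later complete scan or a death could still give an event. That rescue is limited: SAP 4.1.1 ends scheduled scans at radiographic progression, and SAP Section 7 says survival data have not been required since 29 January 2020.

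The protocol's evaluable visit became the SAP's adequate visit, and SAP Section 7 does not list the change. Because the protocol leaves its term undefined, this is a loose end rather than a demonstrated change of method.

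**Conclusion.** The conflict is real and lies in the wording. The narrative and Table 5-1 can give different PFS outcomes for progression first seen on a partial scan, Table 5-2 can date a documented progression too early, and adequacy has two definitions within one section.

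A reader might go further and conclude that PFS is overstated by a definite amount, for instance by comparing event counts with and without such patients. That is not supportable. The counts would be assumed, and a simple ratio of events holds follow-up constant although earlier censoring also removes follow-up. The effect on primary PFS is zero if Table 5-1 governs. It is upward if the narrative is applied literally, and the 3 to 11 points in the illustration depend entirely on the assumed 10% to 30% and on no later rescue.

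Severity is modest. Part 2 will not be run. Part 1 has at most 36 patients (SAP 2.3), PFS is secondary, and SAP 5.1.1 plans no formal test.

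**What to change.** Make three edits to SAP 4.1.2.1 before database lock:

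1. Replace the narrative sentence with: RECIST 1.1 progression at any assessment, complete or partial, scheduled or not, that falls within the data window of the given PFS analysis is a PFS event on the date of that assessment.
2. State that adequacy is used only to choose the censoring date, and give it one definition for both PFS and duration of response.
3. In Table 5-2, date the event for progression found after the last dose at the first documented progression.

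The reference to the data window in the first edit leaves the primary analysis limited to the period before treatment discontinuation. The cost is a few lines of text and one programming condition, with no new data.

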4.2. Safety Endpoints

The safety variables include:

4.2.1. Adverse Events (AEs)

The severity (toxicity grade) of AEs will be graded according to the National Cancer Institute (NCI) Common Terminology Criteria for Adverse Events (CTCAE), Version 4.03.

All AEs will be classified by System Organ Class (SOC) and Preferred Term (PT) according to the Medical Dictionary for Regulatory Activities (MedDRA) version 23.0.

Treatment-emergent AEs (TEAEs) are defined as any AE occurring on or after the first dose of study drug (i.e., C1D-16) until 30 days after the last dose of study drug (G1T38 or Osimertinib, which is later) but prior to the start of survival follow-up. For AEs with an incomplete or unknown/not reported onset date, the imputed onset date will be used to determine if the AE is treatment-emergent.

AEs with onset dates that are partially/completely missing will be imputed as follows:

If the start date has month and year but day is missing,

- If the month and year is the same as the first dose date, then the first dose date will be used, otherwise, the first day of the month will be used

G1 Therapeutics, Inc.
Clinical Study Protocol G1T38-03
Statistical Analysis Plan

If the start date has year, but day and month are missing,

- If the year is the same as the first dose date, then the first dose date will be used, otherwise 1st Jan will be used

If the start date of an event is completely missing, then AE start date is imputed with the first dose date.

After imputation, the imputed start date will be compared with the complete or imputed (if missing or partial) AE stop date. If the imputed start date is later than the stop date, the stop date will be used as imputed start date instead.

Imputation rules for missing or partial AE stop date are defined below:

- If the stop date has month and year but day is missing, the last day of the month will be imputed
- If the stop date has year, but day and month are missing, the 31st of December will be imputed
- If the AE end date is completely missing, the last dose date +30 days will be used as the AE end date.

After the imputation, the imputed AE stop dates will be compared against the date of death, if available. If the date is later than the date of death, the date of death will be used as the imputed date instead.

The following durations will be derived for an AE, AE leading to death, AE leading to discontinuation of any study drug as appropriate and will be displayed in the corresponding AE listings. Cycle 1 Day -16 is used for date of first dose.

- Relative study day for the onset of AE: (AE onset date – date of first dose + 1) if AE onset date is on or after the date of first dose; otherwise (AE onset date – date of first dose)
- Relative study day for the end of AE: (AE stop date – date of first dose + 1) if AE stop date is on or after the date of first dose; otherwise (AE stop date – date of first dose)
- The duration of AE: AE stop date – AE onset date + 1

Drug related AEs are defined as related if causality is related.

Every attempt will be made to obtain complete information for AEs regarding severity (i.e., CTCAE Grade) and relationship to drug; however, in the rare case of missing data, the following conservative approach will be taken for summary purpose. The non-imputed raw data will be presented in AE listings,

- Missing AE grade will be classified as ‘Grade 3’
- Missing AE relationship will be classified as “Related”

G1 Therapeutics, Inc.
Clinical Study Protocol G1T38-03
Statistical Analysis Plan

AEs related to hematological toxicity is of significant clinical interest, Certain PTs will be consolidated into larger categories outside the traditional MedDRA coding guidance. [Table 6-1](#) outlines those terms that will be consolidated.

Table 6-1 Hematologic Preferred Terms to be Consolidated

Presented SOC/PTs in the table	Dictionary SOC/PT
Blood and lymphatic system disorders / Neutropenia	Blood and lymphatic system disorders / Neutropenia
	Investigations / Neutrophil count decreased
Blood and lymphatic system disorders / Anemia	Blood and lymphatic system disorders / Anemia
	Blood and lymphatic system disorders / Anaemia
	Investigations / Red blood cell count decreased
	Investigations / Hemoglobin decreased
Blood and lymphatic system disorders / Thrombocytopenia	Blood and lymphatic system disorders / Thrombocytopenia
	Investigations / Platelet count decreased
Blood and lymphatic system disorders / Lymphocytopenia	Blood and lymphatic system disorders / Lymphocytopenia
	Blood and lymphatic system disorders / Lymphopenia
	Investigations / Lymphocyte count decreased
Blood and lymphatic system disorders / Leukopenia	Blood and lymphatic system disorders / Leukopenia
	Investigations / White blood cell count decreased

In addition, the following gastrointestinal PTs are collapsed in [Table 6-2](#).

Table 6-2 Gastrointestinal Preferred Terms to be Consolidated

Presented term in the table	Preferred Term
Stomatitis	Mouth ulcers
	Mouth ulceration
	Mucosal inflammation
	Stomatitis
	Aphthous stomatitis

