12.3. Part 1 (Phase 1b) Statistical Analyses

The primary analysis is based on the assessment of safety and tolerability endpoints for Part 1 of the study. The data will be analyzed by descriptive statistics. All CIs of data summary will be 2-sided 95%, unless stated otherwise.

Adverse event data will be coded to system organ class and preferred term using MedDRA (Version 17.1 or later). The number and percentage of patients experiencing any TEAE, overall, and by system organ class and preferred term will be tabulated. Adverse events related to treatment will be further summarized by the treatment to which it is attributed (eg, G1T38 or osimertinib). DLTs and withdrawals due to AEs will be summarized or listed; further details with respect to these events can be found in Section 6.1.1.2 and 11.3. Severity will be tabulated based on greatest severity observed for each patient. If a patient experiences an AE more than once during the study, the greatest severity will be tabulated.

Any AE occurring within the defined 30 day follow-up period after the last dose of study drug will be included in the AE summaries. Any adverse events in this period that occur after a patient has received further therapy for cancer (following discontinuation of study drug) will be flagged in the data listings. AEs occurring after the 30 day follow-up period after last dose of study drug will be listed separately, but not included in the summaries.

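### The AE date-imputation sequence in SAP 4.2.1 can move an event known to start after the 30-day window back to last dose + 30 and count it as a TEAE (minor)

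*SAP*

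**What the plan says.** SAP 4.2.1 sets the upper end of the TEAE window as "until 30 days after the last dose of study drug (G1T38 or Osimertinib, which is later) but prior to the start of survival follow-up". For an incomplete onset date, "the imputed onset date will be used to determine if the AE is treatment-emergent".

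The imputation rules that feed this are:

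- Onset with the day missing: the first-dose date if month and year match it; "otherwise, the first day of the month will be used". With only a year recorded, the rule is parallel: the first-dose date or 1 January.
- Stop date absent: "If the AE end date is completely missing, the last dose date +30 days will be used as the AE end date". An imputed stop is capped at death: "If the date is later than the date of death, the date of death will be used as the imputed date instead".
- Cross-check: "the imputed start date will be compared with the complete or imputed (if missing or partial) AE stop date". Then: "If the imputed start date is later than the stop date, the stop date will be used as imputed start date instead".

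Nothing in the stop-date rule separates ongoing AEs from AEs that ended on an unknown date. The medication rule in SAP 5.2.6 does make that separation.

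Protocol 12.3 treats late events differently: "AEs occurring after the 30 day follow-up period after last dose of study drug will be listed separately, but not included in the summaries". SAP Section 7, which records departures from the protocol, does not mention a change here.

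**The concern.** Each rule is ordinary on its own. The trouble is the order in which they act. The start date is checked against a stop date that the SAP itself has supplied, and that supplied date is the closing day of the TEAE window. A late event with no stop date is therefore placed in the window because of a filled-in value, against what the site recorded.

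Safety and tolerability is a primary objective of Part 1, and the TEAE tables (all, serious, related, Grade 3 or higher) are its main display. Events that the protocol sends to a separate listing could appear in those tables. Related SAEs reported after the reporting period (protocol 10.6.1.9) are among the records exposed.

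A second gap lies next to this one. SAP 4.2.1 defines AE duration as stop minus onset plus one, directly after the imputation rules, without saying whether recorded or imputed dates are meant.

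**Working it through.** The plan states no figure to reproduce, so the rules were applied literally to illustrative records. Assumed dates, not from the documents: first dose 4 June 2018, last dose L = 15 July 2020. The window then closes at L + 30 = 14 August 2020. Survival follow-up is assumed not to have started by that day.

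**Step 1: partial onset, no stop date.** Filled stop = L + 30. Final start = the earlier of imputed start and filled stop. TEAE if final start ≤ L + 30.

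| Recorded onset | Imputed start | Final start | TEAE |
|---|---|---|---|
| September 2020 | 1 Sep 2020 (L + 48) | 14 Aug 2020 (L + 30) | yes |
| December 2020 | 1 Dec 2020 (L + 139) | 14 Aug 2020 (L + 30) | yes |
| 2021 | 1 Jan 2021 (L + 170) | 14 Aug 2020 (L + 30) | yes |
| August 2020 | 1 Aug 2020 (L + 17) | 1 Aug 2020 (L + 17) | yes, through the first-of-month rule alone |

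With a recorded stop of 20 September 2020, the September event stays at L + 48 and is not a TEAE. The absent stop date alone changes its class.

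**Step 2: is the reset ever right?** The first of the month, or 1 January, is the earliest date the partial record allows. If even that date is after L + 30, the true onset must be after L + 30. When the onset can instead be imputed to the first-dose date, it cannot fall after L + 30. So whenever the filled stop triggers the reset, the reset contradicts the recorded month or year. The death cap does not alter this: a patient with an AE starting after L + 30 was alive at L + 30.

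**Step 3: how much is due to this rule?** Every last-dose date in 2020 (366 dates) was combined with true post-window onsets, day missing and no stop date.

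- Onset at L + 31 to L + 40 (366 × 10 = 3,660 combinations): 660 (18%) reach the window through the reset; 3,000 (82%) are already there through the first-of-month rule.
- Onset at L + 31 to L + 120 (366 × 90 = 32,940 combinations): 27,539 (84%) through the reset; 5,401 (16%) through the first-of-month rule.

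None stays outside the window. These shares come from evenly spaced dates and do not estimate how often such records occur.

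**Step 4: duration, only if imputed dates are used.** For a complete onset at L + k and no stop date, duration = (L + 30) − (L + k) + 1 = 31 − k days.

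- k = −44 (1 June 2020, ongoing): 75 days, cut at L + 30.
- k = 26: 5 days.
- k = 31: 0 days.
- k = 32: −1 day.
- k = 40: −9 days.

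Negative values arise because the start-versus-stop check applies only to imputed starts.

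**Step 5: the change tested.** With a completely missing stop left unfilled, the September, December and 2021 records keep L + 48, L + 139 and L + 170 and are not TEAEs. The August record is still a TEAE, and durations without a stop date become missing.

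**The case against.** The strongest reply is that few records can meet all the conditions. AEs are routinely reported only to 30 days after last dose (protocol 10.6.1.6). Beyond that, protocol 10.6.1.9 asks for related SAEs, which are reported promptly and followed up. An affected record must start after the window, lack its onset day, have no stop date even in part, and carry a month or year that begins after last dose + 30. This stands. The main routes in are a Post-Treatment visit held as late as day +40 (protocol 9.3) and late related SAEs.

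Other parts of the reply also hold:

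- The error only over-includes; no TEAE is lost.
- Part 1 is descriptive, and the DLT period ends at Cycle 1 Day 28.
- AE listings keep the recorded partial dates, so a reader can see the true month.
- Close to the window, the first-of-month rule brings in more late events than the reset does.

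Caution does not justify the reset itself. The SAP applies a conservative default to missing grade and missing relationship, where the truth is unknown. Here the recorded month or year settles the question.

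A reader might infer that ongoing AEs will certainly be listed with false or negative durations. The documents do not support that. SAP 5.1.2 gives AE date imputation the purpose of determining event status, and SAP 5.2.10 lists non-imputed dates beside the duration. Both lean towards recorded dates. What remains is that the choice is unstated.

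**Conclusion.** The classification error follows from the literal text of SAP 4.2.1 and conflicts with protocol 12.3. Its severity is minor. The number of affected records is not in the documents and is probably small. If one did occur, a patient newly counted in a table row would move that row's rate by 1/6 = 17 or 1/3 = 33 percentage points in a cohort of six or three, always upwards.

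The conclusion assumes that survival follow-up has not begun by last dose + 30. That is the usual case, because it follows a Post-Treatment visit due at day +30 to +40. If it begins on day +30 itself, an event reset to that day is not before it and is not a TEAE. A reader might therefore infer that every late AE with a partial onset is misclassified by this rule, but that goes too far. So does any inference that the DLT evaluation is affected.

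On duration, the finding is an ambiguity with a conditional consequence: durations of ongoing AEs are cut at last dose + 30, and negative values appear for complete onsets at last dose + 32 or later with no stop date, only if imputed dates feed the formula.

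**What to change.** In SAP 4.2.1:

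1. Compare the imputed start date only with a recorded complete or partial stop date, never with one filled in from a completely missing date.
2. Do not impute a stop date for ongoing AEs, in line with the medication rule in SAP 5.2.6.
3. State that AE duration uses recorded dates and is left missing when there is no stop date.

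The cost is about three lines of SAP text and a small change to the AE derivation program. No extra data are needed. The change does not touch late events that enter through the first-of-month rule. There the partial date leaves the onset open, and counting the event is a reasonable default.
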